Two 16-week, randomized, double-blind, placebo-controlled, international efficacy and safety studies of oral treprostinil in subjects with WHO Group 1 PAH already receiving treatment with an ERA, PDE-5i or a combination of both have been conducted. The results did not demonstrate a benefit in exercise testing with median 6MWD at Week 16 (11 meters [Hodges-Lehmann estimate; p=0.072] and 10 meters [Hodges-Lehmann estimate; p=0.089], respectively). Subjects were in WHO functional classification II (~23%) and III (~77%) with either idiopathic or heritable PAH (~66%), collagen vascular disease associated PAH (~29%), or PAH associated with HIV (1%) or congenital heart defect (4%). The mean baseline 6MWD was approximately 340 meters. Approximately 40% of enrolled subjects were receiving both an ERA and a PDE-5i.

Over 824 subjects have received oral treprostinil in a long-term, uncontrolled, open-label ongoing extension study. About 70% of subjects continued treatment with oral treprostinil for at least a year. The mean dose was 4.2 mg BID at one year. The dose of oral treprostinil continued to increase over time with doses (mean \pm SD) of 3.6 \pm 2.7, 4.1 \pm 3.1, and 5 \pm 3.7 mg

BID at 6 (n=649), 12 (n=433), and 24 months (n=238), respectively. In the 522 subjects that completed the 12-month efficacy assessment, their mean 6MWD improved by 24 meters compared to baseline (30 meters in subjects not on another PAH therapy and 20 meters when oral treprostinil was used in combination with an ERA and/or a PDE-5i). Of the subjects that remained in the study, overall survival was 92%, 87%, and 82% at the end of 1, 2, and 3-years, respectively, with progression-free survival (progression defined as death, discontinuation or addition of a PAH therapy) of 74%, 61%, and 47%. Reasons for discontinuation from the study included adverse event (16%), progression of disease (15%), death (13%), and withdrawn consent (7%).

The most frequent adverse events (AEs) associated with oral treprostinil that occurred more frequently than placebo in clinical trials were related to systemic effects that are characteristic of prostacyclin (*e.g.*, headache, diarrhea, nausea, flushing, pain in jaw, pain in extremity).

A comprehensive description of oral treprostinil, including the pharmacology, toxicology, and clinical studies completed to date may be found in the Orenitram Package Insert and current version of the Investigators' Brochure.

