3.3.2.5 Adverse Events

Adverse Events will be recorded throughout the course of the study from the time that each subject and/or caregiver signs the informed consent/assent form until the time screen failure is documented, or until the subject is either discontinued from the study or all Week 24 study assessments have been completed. Each subject/caregiver will be directly questioned for AEs at each scheduled study visit and during required telephone contacts. Subjects/caregivers will also be instructed to spontaneously report all AEs throughout the study. Additionally, a detailed collection of prostacyclin-related AEs will be captured via a standardized diary completed by the subject and/or caregiver each day of the five day inpatient hospital stay during the transition from IV/SC Remodulin to oral treprostinil or all subjects in Cohort 1.

All AEs should be followed until either resolution (or return to normal or baseline values), until they are judged by the Investigator to no longer be clinically significant, or for at least 30 days if the AE extends beyond the final study visit. All AEs meeting the criteria for serious (i.e., serious adverse events [SAEs]) should be followed until resolution, death, or the subject is lost to follow-up even if they are ongoing more than 30 days after completion of the final study visit.

All AEs/SAEs that occur while the subject is on oral treprostinil will be recorded as instructed in this protocol (Section 9.3).

If, at any time, the subject withdraws from the study and/or changes from study drug to commercially available Orenitram, any AEs/SAEs that occur on Orenitram (including product use errors, product quality problems, and therapeutic failures) will be reported following local post-marketing reporting requirements. These events will not be included in the eCRF.

Pulmonary arterial hypertension symptoms (Section 3.3.1.4) and PAH disease related events (Section 9.1.4) should only be recorded as an AE if the event is serious, new, or unusual with respect to intensity, frequency, or duration as compared to symptoms in the subject's medical history; or there is a reasonable possibility that the event was caused by the study drug.

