9.1.1 Adverse Event

An AE is any untoward medical experience occurring to a subject, including any abnormal sign (e.g., abnormal physical exam or laboratory finding), symptom, or disease, temporally associated with the subject's participation in the research, whether or not it is related to the use of the oral treprostinil (study drug).

An AE may include:

- An intercurrent illness, injury, or any other concomitant impairment of the subject's health, as well as abnormal laboratory findings if deemed to have clinical significance.
- A worsening of an existing symptom or condition or post-treatment events that occur as a result of protocol-mandated procedures (e.g., exacerbation of a pre-existing illness following the start of the study or an increase in frequency or intensity of a pre-existing episodic event or condition).

Thus, no causal relationship with the study drug is implied by the use of the term "adverse event".

An AE does not include the following:

- Medical or surgical procedures (e.g., surgery, endoscopy, tooth extraction, transfusion); however, the condition for which the surgery is required may be an adverse event. Planned surgical measures permitted by the study protocol and the condition(s) leading to these measures are not adverse events.
- Day to day fluctuations of pre-existing disease or conditions present or detected at the start of the study that do not worsen.
- Situations where an untoward medical occurrence has not occurred (e.g., hospitalizations for cosmetic elective surgery, social and/or convenience admissions).
- The disease or disorder being studied or a sign or symptom associated with the disease or disorder unless more severe than expected for the subject's condition.

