9.1.4 Adverse Events Anticipated for PAH

Events associated with disease under study:

Expected events that are related to the disease under study are defined in Table 9-1. These events are anticipated to occur in the study population at some frequency independent of drug exposure.

All events that occur during the course of the study that are included on this list and/or felt to be related to the underlying disease under study by the Investigator should NOT be recorded as an AE unless the event is serious or unusual with respect to intensity, frequency, or duration, or there is a reasonable possibility that it may have been caused by oral treprostinil (study drug). These events should be clearly documented in the subject medical record and identified as signs/symptoms of underlying disease under study. All deaths and unplanned hospitalizations, regardless of underlying cause, will be reported as a SAE.
Abdominal pain (Gastrointestinal disorders; ABDOMINAL PAIN)	Hemoptysis (Respiratory, thoracic & mediastinal disorders; HAEMOPTYSIS)
Anorexia (Metabolism and nutrition disorders; DECREASED APPETITE)	Hypoxia (Respiratory, thoracic & mediastinal disorders; HYPOXIA)
Ascites (Gastrointestinal disorders; ASCITES)	Loss of consciousness (Nervous system disorders; LOSS OF CONSCIOUSNESS)
Cardiac arrhythmia (Cardiac disorders; ARRHYTHMIA)	Nausea (Gastrointestinal disorders; NAUSEA)
Cardiac arrest (Cardiac disorders; CARDIAC ARREST)	Edema (General disorders and administration site conditions; OEDEMA)
Heart failure (including exacerbation of) (Cardiac disorders; CARDIAC FAILURE)	Orthopnea (Cardiac disorders; ORTHOPNOEA)
Chest pain (General disorders and administration site conditions; CHEST PAIN)	Pallor (Vascular disorders; PALLOR)
Cardiovascular collapse (Vascular disorders; CIRCULATORY COLLAPSE)	Palpitations (Cardiac disorders; PALPITATIONS)
Cor pulmonale (Cardiac disorders; COR PULMONALE)	Cool extremities (General disorders and administration site conditions; PERIPHERAL COLDNESS)
Cough (Respiratory, thoracic & mediastinal disorders; COUGH)	Pulmonary arterial hypertension, exacerbation of (Vascular disorders; PULMONARY ARTERIAL HYPERTENSION)
Cyanosis (Cardiac disorders; CYANOSIS)	Sudden death (Cardiac disorders; SUDDEN DEATH)
Dizziness (Cardiac disorders; DIZZINESS)	Syncope (Nervous system disorders; SYNCOPE)
Dyspnea at rest (Respiratory, thoracic & mediastinal disorders; DYSPNOEA)	Vasovagal reaction (Nervous system disorders; PRESYNCOPE)

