9.3 FOLLOW UP OF ADVERSE EVENTS

All AEs should be followed until either resolution (or return to normal or baseline values), until they are judged by the Investigator to no longer be clinically significant, or for at least 30 days if the AE extends beyond the final visit. All SAEs that occur during the study will be followed until resolution, death, or the subject is lost to follow-up even if they are ongoing more than 30 days after completion of the final visit. Supplemental measurements and/or evaluations may be necessary to investigate fully the nature and/or causality of an AE or SAE. This may include additional laboratory tests, diagnostic procedures, or consultation with other healthcare professionals. The eCRF pages should be updated with any new or additional information as appropriate.

If, at any time, the subject withdraws from the study and/or changes from study drug to commercially available Orenitram, any AEs/SAEs that occur on Orenitram (including product use errors, product quality problems, and therapeutic failures) will be reported following local post-marketing reporting requirements or Continued Access Plan local reporting requirements (Section 3.3.2.7). These events will not be included in the protocol analysis.

Pulmonary arterial hypertension symptoms (Section 3.3.1.4) and PAH disease related events (Section 9.1.4) should only be recorded as an AE if the event is serious, new, or unusual with

respect to intensity, frequency, or duration as compared to symptoms in the subject's medical history; or there is a reasonable possibility that the event was caused by the study drug.

9.4 **REPORTING RESPONSIBILITIES OF THE INVESTIGATOR**

All SAEs, regardless of expectedness or causality, must be reported to the sponsor within 24 hours of awareness by fax or email

). A completed SAE Notification Report form along with any relevant hospital records and autopsy reports should be provided to Global Drug Safety at United Therapeutics Corporation. A follow-up SAE Notification Report form must be forwarded to the Global Drug Safety Department at United Therapeutics Corporation within 48 hours of the receipt of any new or updated information. The Investigator must also promptly notify their IRB of the SAE, including any follow-up information, in accordance with applicable national regulations and guidelines set forth by the IRB.

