A serious AE is one that represents an actual or potential significant hazard. This includes, but is not limited to, an event that is fatal, life-threatening, permanently or severely disabling, requires or prolongs inpatient hospitalization, is a congenital abnormality (offspring of subject) or is medically significant (important medical events that may not result in death, be life-threatening, or require hospitalization may be considered a serious AE when, based upon appropriate medical judgment, they may jeopardize the subject and may require medical or surgical intervention to prevent one of the outcomes listed in this definition).

Hospitalizations that would not be considered SAEs include those for:

- Routine treatment or monitoring of the study indication not associated with any deterioration in condition (e.g., hospitalization for a routine RHC).
- Treatment which was elective or pre-planned, for a pre-existing condition not associated with any deterioration in condition (e.g., pre-planned operation which does not lead to further complications etc.).
- Treatment of an emergency, in an outpatient setting for an event not fulfilling any of the definitions of serious as given above and not resulting in hospital admission.

CAUSALITY

An estimate of causality between a specified AE and the study drug is made by the Investigator. Several factors should be considered when determining causality. These factors include temporal relationship and response to withdrawal or reintroduction of the study drug. Definitions of the causality categories are as follows:

- NOT RELATED there is not a temporal relationship to study drug administration (too early, or late, or study drug not taken), or there is a reasonable causal relationship between another drug, or concurrent disease and the SAE, or any of the following:
 - An event that precedes the first administration of the study drug
 - An event for which the cause is clearly related to an external event;
 - Temporal relationship to study drug is atypical
 - Is readily explained by an intercurrent illness AND has an expected level of severity, duration, and resolution
 - An alternative explanation (concomitant drug, intercurrent illness) is likely.
- POSSIBLE there is a reasonable causal relationship between the study drug and the SAE. Dechallenge information is lacking or unclear- study drug administration was not modified in response to the SAE, or any of the following:

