 - Has a reasonable temporal relationship to study drug
 - The event has a plausible biological link to the activity of the study drug
 - Is unlikely to be related to an intercurrent illness or has an unexpected degree of severity, duration or complication
 - Unlikely due to an alternative illness or external event (e.g. surgical procedure, accident)
- PROBABLE there is a reasonable causal relationship between the study drug and the SAE. The event responds to dechallenge- the event resolves or improves with modification of study drug administration. Rechallenge (the original study drug dose was not restarted) is not required or any of the following:
 - Has a reasonable temporal relationship to study drug
 - The event has a plausible biological link to the activity of the study drug
 - Not readily explained by an intercurrent illness
 - Not readily explained by external event
 - Improves on discontinuation of study drug
 - If study drug had been discontinued, may recur on reintroduction of study drug

ACTION TAKEN

STUDY DRUG DOSE MODIFICATION*

- Dose Not Changed the dose or regimen of the study drug was not changed.
- Drug Interrupted administration of the study drug was stopped temporarily.
- Drug Withdrawn administration of the study drug was stopped permanently and not restarted.
- Unknown changes to the administration of the study drug cannot be determined.
- Not Applicable

*NOTE: Only the last study drug action should be recorded in the eCRF. For example, if the study drug is withdrawn and then the decision is made to restart, the dose modification of "Drug interrupted" should be reported on the SAE form.

OUTCOME

- Fatal The study subject died.
- Not Recovered / Not Resolved The AE was ongoing at the time of death or at the time the subject was lost to follow up.
- Recovered / Resolved The AE resolved.
- Recovered / Resolved with Sequelae The AE is considered resolved however there is a residual sequelae. Some events do not return to baseline, such as metastasis or progression of disease; however, once these events are determined by the Investigator to be stable or chronic, the Investigator may consider the event to be resolved or resolved with sequelae.
- Recovering / Resolving The AE is improving but is not yet completely recovered/resolved.
- Unknown The outcome of the AE cannot be determined.

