### 11.3 ADVERSE EVENTS

The AEs are collected from the time the informed consent form is signed until study termination. There are a number of AEs that are considered expected events given the underlying disease of study, PAH. These expected events attributable to PAH were not

recorded as an AE unless the event was serious or unusual with respect to intensity, frequency, or duration, or there was a reasonable possibility that it may have been caused by the study drug.

Adverse events will be coded using MedDRA PTs and SOC. All AEs reported in the eCRF will be listed, including non-treatment-emergent and treatment-emergent events.

Non-treatment-emergent AEs are defined as those AEs starting prior to the date of first oral treprostinil dosing. Treatment-emergent adverse events (TEAEs) are defined as those AEs starting on or after the date of first oral treprostinil dosing. The listing will include cohort, subject number, verbatim term, PT, SOC, treatment-emergent status, start/stop date, seriousness, severity, frequency, relationship to oral treprostinil, action taken with oral treprostinil, relationship to background medication, action taken with background medication, and outcome.

The TEAEs will be summarized first in an overall summary, which includes the number of subjects with at least 1 TEAE, at least 1 oral treprostinil attributable TEAE, at least 1 serious TEAE, at least 1 TEAE leading to oral treprostinil discontinuation, at least one background therapy attributable TEAE, at least one TEAE leading to background therapy discontinuation, and any fatal TEAEs. The overall summaries will also include the number of events for each of these categories.

Non-treatment-emergent AEs will be summarized by cohort using PTs. The PTs will be sorted by decreasing overall frequency.

The TEAEs and serious TEAEs will be summarized by cohort using SOC/PT and PT, separately. The summaries will include the number and percentage of subjects reporting and the number of events reported for each SOC/PT and each PT, respectively, for each cohort, in order of decreasing overall frequency, both within SOC and PT.

The TEAEs will be summarized by severity within PT. The TEAEs and serious TEAEs considered attributable to oral treprostinil will be summarized by SOC/PT and PT, as

described above. The TEAEs leading to oral treprostinil discontinuation will be summarized by PT.

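### SAP 11.3 defines treatment-emergent AEs by start date alone, so a pre-dose AE kept as one record that worsens on drug misses the TEAE tables; separately, the sections on recording disease-related events disagree narrowly about new events

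*Protocol*

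**What the plan says.** **TEAE definition.** SAP 11.3 splits AEs by start date: before the date of first oral treprostinil dose is non-treatment-emergent, on or after it is treatment-emergent. There is no clause on worsening, and the protocol gives no TEAE definition. AE recording begins at consent (Protocol 3.3.2.5). Protocol 9.1.1 says an AE may be a worsening of an existing condition. Protocol 9.2 names onset and cessation, intensity, seriousness, relationship and outcome among the items to record. Appendix 15.4 asks for the maximum intensity over the evaluation period.

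**Recording of disease-related events.** The rule appears in several places:

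- Protocol 9.1.4 keeps Table 9-1 events from being "recorded as an AE unless the event is serious or unusual with respect to intensity, frequency, or duration, or there is a reasonable possibility" of causation by oral treprostinil.
- SAP 11.3, in the past tense: such events were not "recorded as an AE unless the event was serious or unusual with respect to intensity", frequency or duration, or possibly drug-caused.
- Protocol 3.3.2.5: such events "should only be recorded as an AE if the event is serious, new, or unusual with respect to intensity, frequency, or duration" compared with the medical history, or if possibly drug-caused. Protocol 9.3 repeats this rule.
- Protocol 9.1.1, the general definition, excludes the disease itself or "a sign or symptom associated with the disease or disorder unless more severe than expected" for the subject's condition.

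**The concern.** Safety and tolerability is the primary objective, AEs are among the primary safety assessments, and there is no control arm. The TEAE tables are therefore the main summary of what happened on drug. An AE that begins mildly in screening and becomes severe, serious or treatment-limiting after first dose bears directly on tolerability. Under a start-date rule, whether it reaches those tables depends on how the site entered it.

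The differing recording rules raise a similar question on a smaller scale: two sites could handle the same first-onset disease symptom differently and each be following the protocol.

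**Working it through.** The plan states no figure on this point, so the check traces cases through the planned outputs and counts terms.

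**1. One case, two ways of entering it.** An AE starts after consent and before first dose, continues, and worsens on drug.

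| Output (SAP 13.1, 13.2) | Worsening entered as a new AE | Kept as one record |
|---|---|---|
| TEAE tables 14.3.1.1, 14.3.1.3 to 14.3.1.12 | in those that apply | in none |
| Table 14.3.1.2, non-treatment-emergent, by preferred term | pre-dose record only | yes, without severity |
| Listing 16.2.7.1, all AEs | yes | yes |
| Listing 14.3.2.3, serious AEs | if serious | if serious |
| Table 14.1.1, Listings 16.2.1.1 and 16.2.1.2 (reason for leaving, SAP 9.1) | if the subject leaves | if the subject leaves |
| Listing 14.3.2.1, deaths within 30 days of last dose | if fatal | if fatal |

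TEAE tables: 1 + 10 = 11 of the 13 numbered 14.3.1.x. The other two are 14.3.1.2 and 14.3.1.13 (disease-related events).

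**2. Pre-dose window.** Protocol 3.6 gives a four-week screening period and 24 weeks of treatment: 4 / (4 + 24) = 14.3%. Screening and Baseline may instead be combined within five days before first dose (Protocol 7.3). Treatment is 24 × 7 = 168 days, so 5 / (5 + 168) = 2.9%. These are shares of time; they do not give the chance that an AE persists and worsens.

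**3. Weight of one subject.** Protocol 10.2 plans 10 to 15 subjects per cohort: 1/15 = 6.7 points and 1/10 = 10 points. This applies only if the subject has no other TEAE of that term.

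**4. Reach of the recording difference.** The rules part only for an event that is first-onset, non-serious, not unusual in intensity, frequency or duration, and judged not possibly drug-caused.

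- Table 9-1: 17 rows × 2 = 34 terms.
- SAP 11.5: 20 entries, of which 18 are single and 2 are pairs (palpitations/arrhythmia, weight loss/gain): 18 + 4 = 22 terms.
- PAH symptom scores (SAP 10.5): fatigue, dyspnea at rest, dyspnea on exertion, edema, dizziness, syncope, chest pain, orthopnea = 8 terms.
- Captured outside the AE tables: 22 + 8 = 30. Remaining: 34 − 30 = 4 (cardiac arrest, cardiovascular collapse, sudden death, exercise intolerance). The first three are ordinarily serious and so would be AEs under either rule.
- Protocol 1.2.4 names six typical drug effects: "headache, diarrhea, nausea, flushing, pain in jaw, pain in extremity". One of the six, nausea, is in Table 9-1.
- The causality exception is wide: under POSSIBLE, Appendix 15.4 accepts that "The event has a plausible biological link to the activity of the study drug". It does not catch everything, because NOT RELATED applies where "there is a reasonable causal relationship between another drug, or concurrent disease and the SAE".

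**The case against.** A start-date rule is explicit and reproducible, nothing in the protocol contradicts it, and non-treatment-emergent AEs are both tabulated and listed. Protocol 9.1.1 counts an increase in the frequency or intensity of a pre-existing episodic condition as an AE, and 9.2 calls for an onset date, so many worsenings will be new records and hence TEAEs. The fields in 9.2 are given as examples, so the lack of a date for a change in intensity proves nothing. The evaluation period in Appendix 15.4 is undefined and could be the interval between visits. All of this stands: the documents do not show that any site keeps one record. What remains is that no section requires a new record, so the classification rests on eCRF conventions that are not shown.

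On the recording rule, 9.1.4 is the specific provision and a first occurrence can be read as unusual in frequency. SAP 11.5 tabulates clinically significant onset or worsening, and exercise capacity is also followed by the walk test, functional class and CPET. SAP 11.3 already states which rule it takes to have been used. This leaves little of the second point beyond a contradiction in wording.

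Three stronger readings are tempting, and the documents support none of them:

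- *Worsening on drug disappears from the report.* It does not; the table in step 1 shows where it remains.
- *The recording rule keeps prostacyclin side effects out of the AE tables.* Five of the six named effects are not on Table 9-1, the causality exception is wide, and Cohort 1 has detailed prostacyclin-related AE collection during the inpatient transition.
- *The primary-endpoint percentage is biased.* Successful transition or maintenance (Protocol 10.3.1) does not use AE classification.

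**Conclusion.** The TEAE point holds as a minor but real weakness. It is conditional on a pre-dose AE being kept as one record and then worsening, becoming serious or leading to drug withdrawal. Such an AE is missing from all 11 TEAE tables although it is visible elsewhere. The number of subjects is unknown; one subject is worth 6.7 to 10 points in a cohort of 15 to 10. The net direction is also unknown: a missed worsening lowers TEAE counts, while an event that occurred earlier on the date of first dose counts as treatment-emergent and raises them.

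The recording point is a genuine contradiction with very little reach. For 30 of 34 terms it changes the table in which the event appears, assuming the onset was clinically significant (SAP 11.5) or was scored at a visit (SAP 10.5). Non-serious exercise intolerance is the one ordinary term in neither place.

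**What to change.** 1. In SAP 11.3, define a TEAE as an AE that starts on or after first dose, or that starts earlier and, on or after first dose, worsens in severity, becomes serious or leads to withdrawal of study drug.
2. Query AEs that start before first dose and continue past it, to establish when any such change occurred. Where timing cannot be established, footnote these AEs in Table 14.3.1.2 with severity, seriousness and action taken.
3. Reconcile Protocol 3.3.2.5, 9.1.1, 9.1.4, 9.3 and SAP 11.3 to one recording rule. If collection is complete, leave the protocol alone and have the SAP disclose that the protocol sections differed.

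**Cost.** Items 1 and 2 need a SAP revision and a small query burden. TEAE percentages may rise slightly, and the wider definition also admits worsening due to PAH itself. A protocol wording change needs an amendment with regulatory and IRB approval (Protocol 13.1) across about 10 centers, and could leave data collected under mixed rules; disclosure in the SAP avoids the amendment.
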